## PROTOCOL SYNOPSIS

Protocol Number	DIAN-TU-001
Protocol Title	A Phase II/III randomized, double-blind, placebo-controlled, cognitive endpoint, multicenter study of potential disease modifying therapies in individuals at risk for and with dominantly inherited Alzheimer's disease.
Clinical Phase	Phase II/III
Investigators	Investigators will be selected based on patient population and clinical research competency. The currently existing DIAN-TU sites will continue to be active for new study drug enrollment and new sites will continue to be identified and qualified.
Study Centers	Approximately 40 sites globally
Study Objective	To assess the safety, tolerability, biomarker and cognitive efficacy of investigational products in subjects who are known to have an Alzheimer's disease-causing mutation by determining if treatment with the study drug slows the rate of progression of cognitive impairment and improves disease-related biomarkers.
Study Population	
Subjects who are either known to have a mutation causing Alzheimer's disease OR who do not know their gene status but are "at-risk" for a dominantly inherited Alzheimer's disease (DIAD) mutation AND who are either 1) cognitively normal and are between 15 years younger (-15) to 10 years older (+10) than their expected age at symptom onset or 2) have mild symptoms of dementia (Clinical Dementia Rating [CDR] 0.5 or 1) and are within 10 years of the onset of symptoms of dementia.
 
Study Design	
This study is an adaptive platform-based study, which allows flexibility to add a new compound to the same protocol, allowing subjects to be randomized to study drug arms open to enrollment, and to maintain a cohort of trial ready subjects with or at risk for DIAD mutations. Subjects have been enrolled to the gantenerumab and solanezumab study drug arms, with each enrolled subject randomized to active drug or the corresponding placebo. Previously, DIAN-TU-001 also included an atabecestat arm. For further information relevant to the atabecestat arm, see earlier versions of the protocol.
 
All subjects enrolled to the gantenerumab and solanezumab arms will continue to be treated with active drug or placebo, while biomarker (e.g., positron emission tomography (PET) imaging, volumetric brain magnetic resonance imaging (MRI), cerebral spinal fluid (CSF), and plasma measures), clinical, cognitive, and safety assessments (including safety MRI scans, vital

	
signs, electrocardiogram (ECG), clinical chemistry, and hematology) are monitored throughout the study period.
 
[REDACTED]
 
The primary efficacy hypothesis is that the active drug group will have a slower rate of progression on the DIAN-Multivariate Cognitive Endpoint (DIAN-MCE) compared to the mutation positive placebos (pooled placebos for both gantenerumab and solanezumab) and the eligible DIAN Observational (DIAN-OBS) study subjects after treatment for a minimum of 4 years. The biomarker and cognitive endpoints may be used to conduct interim analyses in any of the study drug arms; a study drug arm may be stopped early or revised (e.g., dose adjustment or treatment duration) based upon the results of the interim analyses or information from other clinical trials for the same drug, as outlined in each drug-specific appendix.
 
Mutation positive subjects will be randomized in a 3:1 ratio for active drug:placebo. Groups enrolled simultaneously will be balanced by a minimization algorithm including clinical state and stage of disease measures (CDR-SB, years from onset) and other factors (gene type [APP, PSEN1, PSEN2] years of education, age, presence of an APOE <math>\epsilon 4</math> allele, region, study site and gender). Subjects who are mutation negative will be assigned to one of the placebo groups.
 
At the request of participants, mutation negative subjects are included to maintain blinding as to genetic status for those who do not wish to know their genetic status. Mutation negative subjects will not be included in the primary efficacy or futility analyses. Data from mutation negative subjects will be used to develop models for longitudinal changes in biomarkers and cognition in healthy adult controls.

Number of Subjects	
This study will recruit subjects from the Dominantly Inherited Alzheimer Network (DIAN) observational study, a multicenter international study supported by the National Institutes of Health (Grant Number U01-AG032438; [name]), Dominantly Inherited Alzheimer Network Trial Units (DIAN-TU) sites, DIAN-TU partner sites, DIAN Expanded Registry (DIAN-EXR), and families identified by the sites.
 
Recruitment of mutation positive subjects is limited to those with a baseline CDR 0 to 1 (inclusive) with no more than 50% CDR >0 enrolled. Mutation positive groups (active vs. placebo) will be balanced proportionally as to number of asymptomatic (CDR 0) and symptomatic (CDR>0) subjects.

	
For the gantenerumab and solanezumab arms, the recruitment goal was 52 mutation carriers for each active drug group and 34 mutation carriers for the placebo groups combined for a total of 138 mutation carriers. An estimated 72 non-carriers (mutation negative subjects who are unaware of their genetic status, estimated to be about 1/3 of total subjects) would also be recruited. Recruitment was closed once 52 mutation carriers were enrolled in each active drug group and 34 were enrolled in the placebo groups.
 

Main Inclusion Criteria
	
Subjects must meet ALL inclusion criteria based on estimated years from symptom onset (EYO). The main inclusion criteria are as follows:
 
 
• -15 to +10 EYO (secondary prevention population): within -15 to +10 years of the estimated age at symptom onset, or, if symptomatic, within 10 years of their age at symptom onset, CDR 0 to 1, inclusive, known carrier or at 50% risk (affected parent or sibling)
 
• Younger than -15 EYO (primary prevention population): more than 15 years younger (< -15) than estimated age at symptom onset, CDR 0, known carrier or mutation in their family pedigree; if the at-risk parent is deemed a non-carrier at any point, subject will be withdrawn from study
 
• Are able and willing to complete all study-related testing, evaluations, and procedures
 

Main Exclusion Criteria
	
Subjects will be excluded if they have a major or unstable illness or are unable to complete all study related testing. Exclusions include implanted metal that cannot be removed for MR scanning, required anticoagulation therapy and pregnancy.


Route and Dosage Form
	
Route and dosage forms are included in each drug-specific appendix. 
 

Dosage
	
Dosage is included in each drug-specific appendix.

Duration of Treatment
	
For the gantenerumab and solanezumab arms, subjects will continue to receive blinded study drug until every subject concurrently randomized to any blinded study drug arm has received a minimum of 4 years (208 weeks) of treatment or is withdrawn.
 
Based on the recruitment time needed for the gantenerumab and solanezumab arms, the total treatment duration for both blinded study drug

	
arms is expected not to exceed 81 months (6.75 years), with an average duration of 5.3 years.
  
If a study drug arm demonstrates a potential for clinical benefit at the end of the double-blind treatment period, subjects may be offered, if eligible, to continue or start treatment, via an open-label extension (OLE) period in which all subjects will receive active study drug. The OLE period may last up to an additional 2 years (24 months) or until the treatment becomes commercially available in a subject's country, whichever occurs first.

Primary Outcome Measure	
The primary efficacy hypothesis of the study is that the active drug group will have a slower rate of progression on the DIAN-MCE compared to the mutation positive placebos (pooled placebos for both gantenerumab and solanezumab) and the eligible DIAN-OBS subjects after treatment for a minimum of 4 years.
 
The DIAN-MCE consists of the following tests: 1) The Delayed Recall score of the International Shopping List Test, 2) The Delayed Recall score of the Logical Memory IIa subtest from the Wechsler Memory Scale-Revised, 3) The Digit Symbol Substitution Test total score from the Wechsler Adult Intelligence Scale-Revised, and 4) The Mini-Mental State Examination total score. Comparisons will be made between each active drug, mutation positive placebos, and the eligible DIAN-OBS subjects, but not between the active drugs.

Additional Outcome Measures	
Additional outcome measures, which will be further categorized as secondary or exploratory in the drug-specific statistical analysis plans (SAPs), include the following:
 

1. Assess safety and tolerability of each study drug in individuals who have mutations causing dominantly inherited Alzheimer's disease.

2. Biomarker Endpoints used at interim analysis: Assess target engagement of each study drug in individuals who have mutations causing dominantly inherited Alzheimer's disease as measured by the change from baseline to interim analysis for the biomarker measure for each drug. The biomarker endpoints are specified for each drug based on mechanism of action. Comparisons between the active drug and mutation positive placebos will be made at each interim for a study drug arm; however, there will be no comparisons between active drugs.

	
3. Comparisons between each drug and placebo for change in values between baseline and endpoint for the clinical and cognitive measures listed below. [REDACTED]
 

• Clinical measures to be obtained at baseline, and annual visits will be administered at the host DIAN-TU site include:

○ Clinical Dementia Rating™ (CDR), including Clinical Dementia Rating Sum of Boxes™ (CDR-SB) and clinician’s diagnostic assessment

○ Geriatric Depression Scale (GDS)

○ Neuropsychiatric Inventory Questionnaire (NPI-Q)

○ Functional Assessment Scale (FAS)

○ Mini-Mental State Examination (MMSE)

• Cognitive measures to be obtained at baseline and annual visits will be administered at host DIAN-TU site include:

○ International Shopping List Test (12-Item Word List Learning): 3 learning trials, Immediate Recall, 30-min Delayed Recall (Cogstate)

○ Groton Maze Learning Test: Timed Chase Task, 5 learning Trials, Immediate Recall, 30-min Delayed/Reversed Recall (Cogstate)

○ [REDACTED]

○ Trailmaking Test parts A & B

○ WMS-R Digit Span

○ WAIS-R Digit-Symbol Substitution Test

○ Raven’s Progressive Matrices (Set A)

○ Category Fluency (Animals & Vegetables)

○ WMS-R Logical Memory (Immediate & Delayed Recall)

• A subset of clinical and cognitive measures will be administered by the site or home health nurse at 24-week intervals when not the annual visits. This subset includes:

○ International Shopping List Test (12-Item Word List Learning): 3 learning trials, Immediate Recall, 30-min Delayed Recall (Cogstate)

○ Groton Maze Learning Test: Timed Chase Task, 5 learning Trials, Immediate Recall, 30- min Delayed/Reversed Recall (Cogstate)

○ [REDACTED]

--	---

	

○ [REDACTED]

○ Trailmaking Test parts A & B

○ WMS-R Digit Span

○ WAIS-R Digit-Symbol Substitution Test

○ WMS-R Logical Memory (Immediate & Delayed Recall)

○ [REDACTED]

 
4. Additional imaging measures that may be included as secondary or exploratory endpoints as specified in the drug-specific SAP, include the following:
 

a. Change from baseline in amyloid load based on imaging with [C]PiB-PET

b. FDG-PET metabolism in specific regions of interest (e.g., precuneus) in treated group compared with mutation carrier placebos and eligible DIAN-OBS subjects.

c. Tau PET imaging

d. Rate of brain atrophy as measured by cortical thickness of regions of interest, including whole brain volume and ventricular volume (volumetric MRI)

e. Functional connectivity MRI (fc-MRI)

f. [REDACTED]

g. [REDACTED]

h. [REDACTED]

 
5. Additional fluid biomarker measures that may be included as secondary or exploratory endpoints as specified in the drug-specific SAP, include the following:
 

a. Change in total CSF amyloid-beta 1-42 (A<math>\beta</math>42)

b. Change in CSF amyloid-beta peptide concentrations

c. Change in CSF biomarkers: tau and ptau values

d. Plasma amyloid-beta isoform analysis

e. Neurofilament light chain (NfL as measured in plasma and CSF)

 
6. [REDACTED]

--	---

	
[REDACTED]
 
7. Assess longitudinal change in biomarker and cognitive measures in individuals who do not have mutations causing dominantly inherited Alzheimer's disease (mutation-negative placebo group)
 
Additional drug-specific endpoints may be listed in each drug-specific appendix. Refer to the final SAP for drug-specific differentiation of endpoint classification based on the respective drug's target and mechanism of action.

Statistical Considerations	
[REDACTED]
 
Descriptive statistics: Descriptive statistics will be provided for both safety and efficacy variables at each time point collected by treatment groups and across combined placebo groups. Continuous variables (e.g., biomarker values) will be summarized using the number of observations, mean, standard deviation, minimum, lower quartile, median, upper quartile, and the maximum. Categorical variables (e.g., presence or absence of an APOE <math>\epsilon</math>4 allele) will be summarized using the number and percentage in each category.
 
Safety analyses: Safety analyses will include all subjects who consent to participate and are randomized to receive any active study drugs or placebo. Adverse events will be characterized using standard terminology (adverse events, serious adverse events, treatment-emergent serious adverse events). The seriousness and causality of adverse events will be summarized.
 
Interim analyses for biomarker endpoints: Interim biomarker analyses will be conducted for each study drug arm to assess whether the active study drug is engaging its biological target. The timing of the interim analyses may vary for each study drug arm. At each interim, an analysis will be conducted for the biomarker endpoints, comparing the active drug to its own placebo group (direct placebos) or to the mutation positive placebos. Pre-specified definitions for early termination for futility will be drug-specific and based on collection of appropriate biomarker assessments following sufficient drug exposure. Details about the interim analyses are described in each drug-specific appendix.
 
Interim analyses for cognitive endpoints: Interim cognitive analyses may be conducted to assess whether active study drug has achieved significant slowing in cognitive decline. At each interim, an analysis will be conducted for the DIAN-MCE, comparing the active drug to its own placebo group (direct placebo) or the mutation positive pooled placebo group. If the test of the

	
interim analysis is significant, the study drug may be terminated earlier for efficacy. Details about any planned interim analyses are described in each drug-specific appendix.
 
All interim analyses will be conducted on the modified intent-to-treat (mITT) population, which is defined as all subjects who will be randomized, treated, and assessed for their primary cognitive outcomes at least once after the baseline assessment.
 
Efficacy analyses for the cognitive endpoint: All efficacy analyses will be conducted on the modified intent-to-treat (mITT) population. The primary efficacy hypothesis will be tested by comparing the cognitive decline relative to estimated years from symptom onset (EYO) between the active drug, the mutation positive placebos, and the eligible DIAN-OBS subjects using the cognitive multivariate disease progression model (MDPM) developed by the DIAN-TU. The MDPM includes two subject-level random effects to account for the between-subject variability and a model of the mean rate of decline as a function of EYO. Treatment efficacy will be measured as a proportional slowing in decline of the primary cognitive endpoint in active drug compared with the mutation positive placebos and the eligible DIAN-OBS subjects.

Sample Size Considerations	
For the gantenerumab and solanezumab arms, the recruitment goal was for 52 mutation positive subjects per active drug group and 34 mutation carriers for the mutation positive placebo group to allow for 5% annual attrition during the minimum 4-year double-blind treatment period. Assuming 5% annual attrition rate, at the end of the 4-year study, there will be approximately 42 subjects on each active treatment and 27 mutation positive placebos. Power analysis for the biomarker endpoints suggests that this sample size will provide over 99% power to detect calculated effect sizes for changes in PiB and CSF total A<math>\beta</math> 1-42 (A<math>\beta</math>42). Power analysis for the DIAN-MCE suggests that 42 mutation positive subjects in the active drug groups, 27 mutation positive placebos, and eligible DIAN-OBS subjects will provide over 90% power to detect a 40% effect size (slowing of decline in cognition for active drug in comparison to placebo) when the last subject randomized to the study drug arm reaches the end of the minimum 4-year double-blind treatment period.

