### 3.7 Safety Endpoints

This study will assess safety and tolerability in individuals at risk for dominantly inherited AD. Safety endpoints used will be the incidence and severity of treatment-emergent adverse events (TEAEs), serious adverse events (SAEs) and treatment discontinuations. Analysis will be on an intent-to-treat basis. Clinical laboratory evaluations, vital signs, and 12-lead ECGs will also be measured throughout the study.

Amyloid-related imaging abnormalities (ARIA) are a safety endpoint in studies of DAT. Based on the assigned study drug arm, this study may include MRI scans every few months to assess for ARIA changes. ARIA can occur as either cerebral edema (ARIA-E) or as hemorrhages (ARIA-H), typically microhemorrhages, but larger hemorrhages and frank infarction have also been reported (Sperling, Salloway et al. 2012). MRI scans will be analyzed for ARIA changes at the Mayo Clinic Aging and Dementia Imaging Research (Mayo-ADIR). The number of microhemorrhages (ARIA-H, including both hemorrhages and hemosiderin deposits) and size of

areas of edema (ARIA-E) will be monitored at entry and throughout the trial. Incidence of ARIA and comparison to placebo will be made.

A report of new ARIA changes in a subject will trigger a review by the DIAN-TU Medical Director or designee, Project Arm Leader (PAL), and site principal investigator. This review will include contact with the subject or caregiver to assess for any symptoms associated with the changes and discussion with the central readers. The PAL, as a site independent neurologist, will help ensure consistency of decisions within a study drug arm across sites during the study. See each drug-specific appendix for drug-specific ARIA algorithms. The DIAN-TU Medical Director will ensure consistency across study drug arms and will have final decision-making authority on changes in dosing of study drug or safety monitoring; this decision should be received by the site within 7 days of the report of the new ARIA changes, but no later than the day prior to the planned administration of the next dose of medication. A similar process will be followed if a follow-up MRI shows worsening of a previously reported ARIA.

Additional assessments based on drug-specific safety concerns are detailed in each drug-specific appendix (Appendices 3 and 4).

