An independent Data Safety Monitoring Board (DSMB) will assess safety data periodically throughout the study. The DSMB will have timely access to data, including clinical laboratory values, ECGs, MRI results, and clinical and cognitive testing scores; this will include access to unblinded data when requested. The DSMB will monitor the incidence of ARIA and comparison to placebo. See section 7.9 and the DSMB charter for additional information.

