Amendment 8 includes a revised safety MRI schedule. A safety MRI will be scheduled 1 week ( $\pm$  4 days) after the second dose of each titration step (225 mg, 450 mg, 675 mg, 900 mg), unless otherwise indicated by the ARIA-E and ARIA-H management algorithms (section 1.14). Subjects

may be at different titration steps and time points in the schedule of visits at the time of this amendment and should be scheduled based upon their current titration step/stable dose at the time of the amendment. For titration step #4, the final titration step (1200 mg), safety MRIs will be scheduled 1 week ( $\pm$  4 days) after every third dose (or approximately every 3 months) for the next 6 doses unless otherwise indicated by the algorithm ARIA-E and ARIA-H management algorithms. Although the titration schema was designed to reach the target dose of 1200 mg administered every 4 weeks, the target dose may not be achieved as otherwise dictated by the ARIA-related management algorithms or more conservative action by the site principal investigator/sponsor. The stable dose is defined as the maximum dose the subject will remain at for the duration of the trial based on safety. Once a subject reaches their stable dose, safety MRIs will be scheduled after every 6 doses (or approximately every 6 months) for the remainder of the trial unless otherwise indicated by the algorithm (i.e., 6 doses, MRI, 6 doses, MRI, etc.). The annual MRI assessment can fulfill these requirements as long as the MRI reading is reviewed prior to dosing at that visit; however, the safety MRIs following every sixth dose of 1200 mg must occur regardless of when the annual MRI is scheduled.

Safety MRIs will be performed at the same field strength throughout the study, and if possible on the same scanner. All MRIs will be centrally read.

The MRI schedule may be changed according to the ARIA-related dosing intervention algorithm (see tables in section 1.14) or per individual request by the site principal investigator or delegated sub-investigator, Project Arm Leader (PAL), or Medical Director or designee.

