### **1.13 Drug-specific Safety Concerns**

#### **1.13.1 Amyloid-related Imaging Abnormalities (ARIA)**

Amyloid-related imaging abnormalities (ARIA) are a special safety endpoint in studies of Alzheimer's immunotherapies, including both active and passive immunization. Since compounds studied in DIAN-TU are investigational, this study includes frequent MRI scans to assess for ARIA changes. ARIA can occur as either cerebral edema (ARIA-E) or as hemorrhages

(ARIA-H), typically microhemorrhages, but larger hemorrhages and frank infarction have also been reported (Sperling et al., 2012). The number of microhemorrhages will be monitored at entry and throughout the trial.

The frequency of MRI monitoring will be reduced to annually after the first two years of the study. Results from two large Phase 3 trials in mild-to-moderate AD (LZAM and LZAN) and one Phase 3 trial in mild AD (LZAX) have been analyzed and have shown no statistically significant differences between solanezumab and placebo on safety MRI parameters. The reduced frequency of MRI monitoring here will closely match extension studies (LZAO and open-label extension period of LZAX) with solanezumab.

Following the approval of Amendment 7, the dose escalation process will begin. Subjects may be at different time points in the schedule of visits when initiating dose escalation, but all must have had at least 2 doses at 400 mg. Prior to escalation to the 800 mg dose level, subjects will sign a new ICF.

With other investigational anti-A $\beta$  antibodies, most cases of dose-related ARIA-E have occurred after 2 doses of an increased dose (Sperling et al. 2012). Therefore, an additional safety MRI will be conducted before the first dose of 1600 mg (approximately 1 week after the second dose of 800 mg). The annual MRI assessment can fulfill this requirement. The safety MRI must be reviewed prior to dose escalation to 1600 mg.

Although the dose escalation schema was designed to reach the target dose of 1600 mg every 4 weeks, the target dose may not be achieved as otherwise dictated by the ARIA-related intervention algorithms or more conservative action to be discussed by the site and the sponsor. The MRI schedule may be changed according to the ARIA related dosing intervention algorithm (see tables in section 1.15) or per individual request by the site principal investigator or delegated sub-investigator, Project Arm Leader (PAL), or Medical Director or designee.

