### **3.3.18 Safety Magnetic Resonance Imaging (MRI)**

A series of 6 safety MRI visits will be scheduled over the first 2 years of the double-blind treatment period. Safety MRIs on 3T scanners will be done primarily to monitor for ARIA.

*Location:* Safety MRIs may be done at the host DIAN-TU site or, for subjects who live at a distance from the host DIAN-TU site, safety MRIs may be performed at an ADNI/ADCS site if possible or at a 3T scanner near the subject's home.

*Timing:* 13, 25, 37, 65, 77, and 89 weeks +/- 7 days from Visit 2 (calculated from day of first dose). Sites must ensure that study visits are scheduled so that MRI images are uploaded and available for central read at least 10 working days before next administration of study drug for parenterally administered drugs.

*Procedures:* Safety MRIs on 3T scanners will be done primarily to monitor for ARIA. See section 6.1.16 of the main protocol for more information. Detailed requirements are provided in the *MRI Technical Manual*.

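### Against pooled placebo, transient ARIA-E is ascertained unequally: after about year 2 the gantenerumab arm is scanned two to three times as often as the solanezumab arm, and each placebo group follows its own arm's schedule

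*Protocol*

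**What the plan says.** **Comparator**

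- Protocol section 2 (Study Objective) assesses the safety of each drug against the mutation positive placebos. The glossary defines these as direct plus concurrently randomized placebos.
- The Synopsis (Statistical Considerations), with nearly the same text in section 8.1, says: "Descriptive statistics will be provided for both safety and efficacy variables at each time point collected by treatment groups and across combined placebo groups".
- Section 3.7 says of ARIA: "Incidence of ARIA and comparison to placebo will be made". It adds: "The DSMB will monitor the incidence of ARIA and comparison to placebo". Neither sentence says which placebo. Section 8.2 says that ARIA will be analysed and names no comparator.
- Section 4.2.1 of Appendix 3 and of Appendix 4 each gives 17 direct placebos in a pooled group of 34 carriers.

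**MRI schedule**

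- Solanezumab, years 1-2 (Appendix 4, 3.3.18): "A series of 6 safety MRI visits will be scheduled over the first 2 years of the double-blind treatment period", at "13, 25, 37, 65, 77, and 89 weeks +/- 7 days from Visit 2", plus the annual MRIs.
- Solanezumab afterwards (Appendix 4, 1.13.1): "The frequency of MRI monitoring will be reduced to annually after the first two years of the study". On dose escalation "an additional safety MRI will be conducted before the first dose of 1600 mg", and the annual MRI may serve for it.
- Gantenerumab, first two years at the starting dose (Appendix 3, 1.13.1): safety MRIs about one week after doses 2, 4, 6, 9, 17 and 22, plus the annual MRIs.
- Gantenerumab under Amendment 8 (Appendix 3, 1.13.1 and Table 5): a scan after the second dose of the 450, 675 and 900 mg steps and after doses 3 and 6 at 1200 mg. The rule for later scans, which applies until trial end, begins: "Once a subject reaches their stable dose, safety MRIs will be scheduled after every 6 doses (or approximately every 6 months) for the remainder of". At 1200 mg, each sixth-dose scan is required whatever the timing of the annual MRI.

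**The concern.** ARIA-E is found on MRI and can resolve between scans, so the number of cases detected depends on how often subjects are scanned. Subjects on placebo follow the MRI schedule of the arm to which they were assigned. Each direct placebo group therefore matches its active group in scheduled scanning, but the pooled group does not match either one.

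Against pooled placebo, gantenerumab would be set against controls of whom half are scanned less often than it is, which inflates its ARIA-E ratio. Solanezumab would be set against controls of whom half are scanned more often, which deflates its ratio. The two drugs would be misjudged in opposite directions on a safety endpoint that the protocol singles out. The protocol defines direct placebos and offers them by name for the interim analyses, but not for ARIA.

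**Working it through.** **1. Reproduce the schedules.** The listed solanezumab weeks (13, 25, 37, 65, 77, 89) number six, as stated. Gantenerumab doses 2, 4, 6, 9, 17 and 22 also number six. At 4-week dosing, the scan one week after dose d falls at week (d - 1) x 4 + 1, that is weeks 5, 13, 21, 33, 65 and 85. Both arms add annual MRIs at weeks 52 and 104, so the original schedules have equal scan counts in years 1-2. Six doses are 24 weeks, or 24/52 x 12 = 5.5 months, which agrees with the stated interval of about 6 months.

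**2. Scan rates after year 2, stable dose.**

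- Gantenerumab: 52/24 = 2.17 a year if the annual MRI counts as one of these scans, and 2.17 + 1 = 3.17 if it is additional.
- Solanezumab: 1 a year.
- Ratio: 2.2 to 3.2. During gantenerumab titration, with a scan every second dose (8 weeks), the rate is 52/8 = 6.5 a year, or 7.5 with the annual MRI.

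**3. Detection in years 3-4 with no drug effect.** Assume that an episode lasts D weeks and starts at random. It is found if a scan falls within D weeks of onset, so the detection probability is the weeks lying within D weeks before a scan, divided by 104. Appendix 3 (1.4, NN19866) reports resolution 1-4 months after gantenerumab was stopped; D = 4, 9 and 17 weeks spans that range. Illustrative gantenerumab scans are at weeks 132, 156, 180 and 208 (annual absorbed) or 125, 149, 156, 173, 197 and 208 (annual additional). Solanezumab scans are at weeks 156 and 208.

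| D | Gantenerumab, absorbed | Gantenerumab, additional | Solanezumab | Ratio k |
|---|---|---|---|---|
| 4 | 16/104 = 0.15 | 24/104 = 0.23 | 8/104 = 0.08 | 2.0, 3.0 |
| 9 | 36/104 = 0.35 | 52/104 = 0.50 | 18/104 = 0.17 | 2.0, 2.9 |
| 17 | 68/104 = 0.65 | 86/104 = 0.83 | 34/104 = 0.33 | 2.0, 2.5 |

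**4. Ratio to pooled placebo.** With 17 and 17 controls, pooled detection is (k + 1)/2 relative to the solanezumab schedule.

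- Gantenerumab: 2k/(1 + k), which is 1.33 at k = 2 and 1.50 at k = 3.
- Solanezumab: 2/(1 + k), which is 0.67 at k = 2 and 0.50 at k = 3.
- Against its own direct placebo, each drug's ratio is 1.0, before any ARIA-triggered extra scans.

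**5. Years 0-4.** Add the years 1-2 scans from step 1 and count covered weeks out of 208, gantenerumab (absorbed, additional) against solanezumab:

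- D = 4: 48, 56 against 40, so k = 1.20, 1.40.
- D = 9: 102, 118 against 90, so k = 1.13, 1.31.
- D = 17: 165, 183 against 138, so k = 1.20, 1.33.

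Across k = 1.13 to 1.40 the gantenerumab ratio is 1.06 to 1.17 and the solanezumab ratio 0.94 to 0.83.

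**6. Persistent lesions.** If a microhemorrhage does not resolve, both arms find it by the next annual MRI. Then k = 1.0 and only the date of detection differs.

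**7. Absolute size.** Appendix 4 (1.6) gives ARIA-E in 0.3% of placebo patients in the Phase 3 studies in mild AD. If that rate held here, which is an assumption, 34 x 0.003 = 0.1 event would be expected among the pooled placebos.

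**The case against.** The strongest reply is that no sentence plans an ARIA test against pooled placebo. The descriptive sentence gives results by treatment group as well as combined, direct placebos are a defined group, and the comparator for an ARIA table is commonly left to the SAP. Part of this stands: the bias arises only where ARIA-E is set against the pooled group. It does not remove the point, because section 2 itself names the pooled mutation positive placebos as the safety reference, and following that text produces the mismatch.

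Further objections that stand:

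- A by-visit summary at the annual MRIs is balanced. The distortion needs a count that includes the scans between them.
- The 1-4 month duration comes from patients who stopped gantenerumab at 200 mg IV. Applying it to ARIA-E on placebo is an assumption.
- With very few placebo ARIA-E events, a multiplicative distortion has little absolute effect.
- Direct placebo halves the controls for a rare event, so there is a real trade between precision and equal ascertainment.

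A reader might also infer that a real solanezumab signal would be hidden from the DSMB. The documents do not support that. The DSMB reviews unblinded MRI findings quarterly (section 7.9), each new definite ARIA finding triggers individual review (Appendix 4, 1.14), and unscheduled MRIs are allowed whenever a clinical concern arises (Appendix 4, 1.13.1). Nor would a different placebo denominator reveal cases that annual scanning of the active group had missed.

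**Conclusion.** The point holds for transient ARIA-E wherever it is compared with pooled placebo. With no drug effect, the detected ratio after year 2 is about 1.3 to 1.5 for gantenerumab and 0.5 to 0.7 for solanezumab, and about 1.06 to 1.17 and 0.83 to 0.94 over years 0 to 4.

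These figures assume ARIA-E lasting 1-4 months, random onset at a constant rate, the original schedules in years 1-2, stable dose afterwards, and a 17:17 placebo split. Titration times vary by subject, and the gap is wider while gantenerumab subjects titrate. The four-year window also understates later exposure: mean treatment is 64 months, or 64 x 52/12 = 277 weeks, so (277 - 104)/277 = 62% of it falls after week 104, without attrition.

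Two stronger readings should be resisted. The first is that all ARIA comparisons are biased; cumulative ARIA-H is nearly unaffected, because both arms have annual MRI. The second is that the years 3-4 ratios describe the whole trial; they do not, because the two arms start with equal scan counts.

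**What to change.** In sections 3.7, 8.1 and 8.2, name each arm's direct placebo, which shares its MRI schedule, as the comparator for ARIA-E incidence. Where combined placebo is also shown, add a version that counts only findings on MRIs scheduled in both arms (baseline and annual visits), and report scans per subject-year by group. Apply the same rule to the ARIA tables for the DSMB, and align the safety reference in section 2.

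The cost is wording and table programming, with no new data. The downside is about 17 rather than 34 control carriers, and so wider intervals. No MRI schedule, dose or clinical rule changes.
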